# 10.2.3 Collection and reporting of SAEs

For any SAE during the trial, the investigator should actively take appropriate action to ensure the safety of subject, no matter whether the SAE is related to study vacccine. The investigator should report to Fosun whthin 24 hours of being informed of the SAE.

For reports of deaths, the investigator shall provide the Fosun and the ethics committee with other information as required, such as an autopsy report and a final medical report.

The investigator shall sign and read the clinical trial safety information provided by the sponsor in a timely manner, and shall consider the treatment of the subject, whether to adjust accordingly, communicate with the subject as soon as necessary, and report to the ethics committee the suspicious and unexpected serious adverse reactions (SUSAR) provided by the sponsor.

The investigator shall follow up the SAE according to the protocol requirements, and provide a detailed, written follow-up report within 24 hours after receiving the follow-up information, in the same manner as above.

The sponsor or its representative shall evaluate and report the SAE (including SUSAR) in the clinical trial in accordance with the latest applicable regulatory requirements for the clinical trial of the investigational product.

Contacts of serious adverse event reports:

Table 5 Contact information for serious adverse events reporting

Unit	Phone	Reporting way
Pharmacovigilance Department of Beijing Fosun		Email: [contact]
Jiangsu Center for Disease Control and Prevention		

# 10.3 Assessment of safety parameters

# 10.3.1 Assessment of intensity

Reaction signs and symptoms involved in the grading scale will be graded respectively by the investigator according to the Guidelines for Adverse Event Classification Standards for Clinical

Trials of Preventive Vaccines of NMPA (Appendix B) and FDA (Appendix C). AEs uninvolved in the grading scale will be graded clinically by the investigator according to following criteria. Grading and seriousness need to be assessed independently for each AE recorded on the CRF.

Mild	Grade 1	Lasting for a short time (<48h) or slight discomfort, which do not influence activity and no treatment is needed.
Moderate	Grade 2	Mild or moderate limitation of activity, which may require hospital visit, does not require or only requires mild treatment.
Severe	Grade 3	Obvious limitation of activity, which requires hospital visit and treatment, possibly requires hospitalization.
Critical	Grade 4	Possibly life-threatening; serious limitation of activity, which requires intensive care
Death	Grade 5	

# 10.3.2 Relationship to investigational drug

Relatedness (causality) to vaccine will also be assessed by the investigator. The relationship between each AE, including solicited systemic AEs (solicited local AEs are considered as related) to trial vaccine(s) will be assessed using the following categories:

- Definitely related: There is reasonable time relationship between drug administration and the occurrence of adverse event; after drug withdrawal, the adverse reaction disappears or is rapidly relieved and improved (ie, dechallenge positive); when the drug is administrated again, the adverse event appears again (ie, rechallenge positive) and may get worse obviously; meanwhile, there is evidence from investigator brochure or literature data; besides, influence from original disease and other confounding factors are excluded.
- Probably related: There is no history of repeated drug administration. The rest are the same as those for "definitely related", or even if there is drug combination, the possibility of adverse reaction resulted from drug combination is generally excluded.
- Possibly related: There is close relationship between drug administration and adverse event, which can also be proved by literature data. However, there may be more than one drug which causes adverse event or the original disease progression cannot be excluded.
- Possibly unrelated: The relationship between adverse event and medication time is not close. The clinical manifestation is not consistent with the known adverse events of the drug. If the original disease develops, it may have the similar clinical manifestation.
- Unrelated: No drug is administrated, or there is no association between drug administration and the occurrence time of adverse event or there is other definite reason which results in adverse event.

Related, probably related and possibly related are listed as related to the investigational vaccine.

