# **5.1.3** Exploratory objective

## 5.2 Endpoints

# 5.2.1 Primary endpoints

*Safety and tolerability of BNT162b1, as determined by:* 

- Occurrence of solicited local reactions in the subjects (eg, vaccination sites: pain/tenderness, erythema/redness, induration/swelling) during the 14-day after each dose of BNT162b1 or placebo.
- Occurrence of solicited systematic reactions (eg, nausea, vomiting, diarrhea, headache, fatigue, myalgia, arthralgia, chills, loss of appetite, malaise, and fever) during 14-day after each dose of BNT162b1 or placebo.

• Occurrence of AE associated with vaccination in subjects during the 21-day period after prime vaccination and the 28-day period after boost dose of BNT162b1 or placebo.

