#### 10.1.2 Solicited reactions

The occurrence of selected indicators of safety will be measured/collected for 14 days after each vaccination (including the days of vaccine vaccination), see details in following **Table** 5.

Table 4 Solicited local and systemic reactions

Local reactions (vaccination site):	Pain/tenderness
	Erythema/redness
	Induration/swelling
Systemic reactions:	Fever (a)
	Nausea
	Vomiting
	Diarrhea

Headache
Fatigue
Myalgia
Arthralgia
Chills
Loss of appetite
Malaise

(a) Based on recorded body temperature, fever is defined as axillary temperature ≥37.3°C.

The intensity of solicited safety parameters will be assessed respectively as described in grading scale of Appendix B and C.

Solicitation adverse reactions: there is at least a reasonable possibility of a causal relationship between vaccines and adverse events, that is, causality cannot be ruled out.

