# 10.3.4 Expectation assessment of adverse events

An unexpected adverse reaction refers to an adverse reaction with the nature, severity, consequence, or frequency different from the expected risks described in the current relevant data of the investigational vacccine (such as investigator brochure or another document). Investigator brochure is used as the main document to provide safety reference information to judge whether an adverse reaction is expected or unexpected.

Suspected unexpected serious adverse reaction (SUSAR): refers to a suspected and unintended serious adverse reaction with the nature and severity of clinical manifestations beyond the existing data and information in investigator brochure of investigational vacccine, package inserts of drugs on market or summary of product characteristics, etc.

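### The causality scale in Protocol 10.3.2 ties every related category to brochure or literature evidence, so new unsolicited reactions may be under-counted as related

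*Protocol*

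**What the plan says.** Protocol 10.3.2 gives the investigator five causality categories and states which count: "Related, probably related and possibly related are listed as related to the investigational vaccine".

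- **Definitely related** lists several conditions together, among them "meanwhile, there is evidence from investigator brochure or literature data".
- **Probably related** drops the repeat-administration history and then says "The rest are the same as those for" the top category. A further clause covers combined drugs.
- **Possibly related** begins "There is close relationship between drug administration and adverse event, which can also be proved by literature data", and adds that another drug or the underlying disease may be responsible.
- **Possibly unrelated** requires timing that is not close, and also says "The clinical manifestation is not consistent with the known adverse events of the drug".
- **Unrelated** covers no administration, no association in time, or another definite cause.

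Solicited local events are related by rule in the same section.

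Neighbouring sections use other tests. For solicited adverse reactions, 10.1.2 says "there is at least a reasonable possibility of a causal relationship between vaccines and adverse events, that is, causality cannot be ruled out". Section 10.3.3 uses a reasonable possibility for trial procedures. Section 10.3.4 treats comparison with the brochure as a separate expectedness step, and defines a SUSAR as a suspected serious reaction "with the nature and severity of clinical manifestations beyond the existing data and information in investigator brochure".

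The third primary endpoint in Protocol 5.2.1 depends on relatedness: "Occurrence of AE associated with vaccination in subjects during the 21-day period after prime vaccination", with a matching 28-day period after the boost.

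**The concern.** A causality scale should ask whether the injection could have caused the event. Whether the event was already known is a different question, which 10.3.4 handles. Section 10.3.2 puts the second question inside the first. An investigator who applies it as written has no related category for a reaction that is new to the brochure and the literature.

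Protocol 4.3.1 says that clinical experience with BNT162b1 is very limited, so reactions not yet described are realistic, and a Phase I trial is where they should be found. If such events are not rated related, they are missing from one of the three primary endpoints and do not meet the relatedness condition that opens the DLT rule in 6.6. Investigators who read the scale differently would also rate the same event differently, which adds noise to the related-AE counts.

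**Working it through.** The check is textual. Take one test event: unsolicited, closely timed to the injection, with no other cause, and described in neither brochure nor literature.

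| Category in 10.3.2 | Literal conditions | Does the test event fit? |
|---|---|---|
| Definitely related | Timing, positive dechallenge and rechallenge, brochure or literature evidence, no confounding | No: the evidence is absent |
| Probably related | As above without repeat administration, or a combined-drug clause | No, if the evidence condition carries over |
| Possibly related | Close relationship that literature can also prove; a competing cause not excluded | No, if the literature clause is a condition |
| Possibly unrelated | Timing not close; not consistent with known events | Only in part: the timing is close |
| Unrelated | Not given, no time association, or another definite cause | No |

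The event falls in a gap.

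**Against the other standards.** Under the reasonable-possibility wording of 10.3.3 (written for procedures) or 10.1.2 (written for solicited reactions), the same event would count. Under 10.3.4 a SUSAR must be both suspected and beyond the brochure. A causality scale that asks for brochure or literature support makes that pair hard to satisfy for an event of a new nature.

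**Where the investigator's rating is used:**
- third primary endpoint (5.2.1);
- AEs associated with BNT162b1 up to Months 3, 6 and 12 (5.2.2);
- DLT suspension rule (6.6). Some triggers need only one event, such as a possibly related Grade 4 AE within 7 days;
- treatment-emergent status more than 28 days after the last vaccination (Protocol 10.1.1), and collection after that time (10.2.2);
- related-AE tables (Protocol 13.1.4; SAP 7.6.1).

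**Where it is not used:**
- solicited local and systemic reactions as primary endpoints (5.2.1);
- SAE reporting (10.2.3) and the SAE endpoint to Month 12 (5.2.2);
- AESI reporting (10.1.4);
- SRC review of TEAEs (11.1);
- the SAP definition of a TEAE (7.1.2) and the any-TEAE tables (SAP 7.6.1).

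**Numbers.** The plan's one design figure is in Protocol 13.3: n = 24 and a TEAE rate of 8% give 1 − (1 − 0.08)^24 = 0.8648, the stated 86.5%. It reproduces. It concerns any TEAE, so the causality scale does not change it for events inside the collection window.

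The documents do not say how often a new reaction would be left out of the related count. As an illustration only, let a vaccine-caused reaction have a true rate of 8%, and let a fraction f of its occurrences not be rated related. The chance of at least one event rated related in 24 subjects is 1 − (1 − 0.08(1 − f))^24:

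- f = 0: 86.5%
- f = 0.25: 1 − 0.94^24 = 77.3%
- f = 0.5: 1 − 0.96^24 = 62.5%
- f = 0.75: 1 − 0.98^24 = 38.4%

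The values of f are assumptions, and nothing in the documents favours one of them.

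**The case against.** The strongest reply is that the wording is loose rather than restrictive. The literature clause under Possibly related can be read as permissive. Probably related has an alternative branch. Literature is not limited to this product, and Protocol 4.3.1 itself draws on related RNA products and other vaccines. An experienced investigator would probably rate a striking, well-timed event as possibly related. This stands as a limit on the claim, but it does not remove the problem: the text supports both readings, and a primary endpoint depends on which one the assessor takes.

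A reader might infer several stronger things that the documents do not support:

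- **That a new reaction can never be rated related, or is directed to Possibly unrelated.** The permissive reading is available, and Possibly unrelated also requires timing that is not close.
- **That such an event cannot become a SUSAR.** Under 10.2.3 the sponsor or its representative evaluates SAEs, including SUSARs, and receives every SAE whatever its relatedness. Nothing binds that evaluation to the investigator's scale.
- **That it disappears from late follow-up.** SAEs and AESIs are reported whatever the cause, and Table 2 marks AE recording through Visit 12. At most, non-serious events that are not AESIs are exposed.
- **That 10.1.2 sets a general rule that 10.3.2 breaks.** Its sentence concerns solicited reactions. The clearer conflicts are with 10.3.3 and 10.3.4.

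The reply is also right that other review continues. The SRC sees TEAEs without a relatedness filter, 4.3.1 lets the investigator request ad hoc review of a worrying pattern, and the IDMC reviews safety data. SAP 7.6.1 tabulates any, related and unrelated TEAEs by group, and SAP 7.1 plans no formal testing, so a new signal would remain visible there.

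**Conclusion.** The concern holds as a conflict in wording with a real but bounded effect. On a literal reading, 10.3.2 has no related category for a closely timed unsolicited event of a new kind with no other cause, and neither unrelated category fits it cleanly. The section mixes causality with expectedness and cannot be squared with 10.3.3 and 10.3.4.

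The exposure covers one of three primary endpoints, the related-AE endpoint to Month 12, the related-AE tables, the relatedness condition of the DLT rule, and late collection of non-serious events that are not AESIs. How many events would be affected cannot be determined from the documents: it depends on how many reactions are new and on how investigators read the text. The percentages above 0 for f are illustrations, not estimates. A reader might infer that the plan's 86.5% collapses for new reactions. It does not, because that figure counts any TEAE.

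**What to change.** Reconcile 10.3.2 with 10.1.2, 10.3.3 and 10.3.4:

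1. Use one standard for relatedness: a reasonable possibility that the study injection caused the event.
2. State in Definitely, Probably and Possibly related that brochure or literature evidence is supportive but not required.
3. Leave comparison with the brochure to the expectedness assessment in 10.3.4.
4. Apply the revised wording to all AEs in all arms while assessors are blinded, before the Day 50 unblinding.

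The cost is a wording change in one section, site training, and blinded re-assessment of any AEs already rated. Somewhat more AEs will be rated related, and this can bring more events under the relatedness condition of the DLT rule, so the SRC should be told. No DLT threshold or dose changes.

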# 10.3.3 Relationship to trial procedures

Relationship (causality) to trial procedures should be determined for all AEs.

The relationship should be assessed as "Yes" if the investigator considers that there is reasonable possibility that an event is due to a trial procedure. Otherwise, the relationship should be assessed as "No".

# 10.3.4 Expectation assessment of adverse events

An unexpected adverse reaction refers to an adverse reaction with the nature, severity, consequence, or frequency different from the expected risks described in the current relevant data of the investigational vacccine (such as investigator brochure or another document). Investigator brochure is used as the main document to provide safety reference information to judge whether an adverse reaction is expected or unexpected.

Suspected unexpected serious adverse reaction (SUSAR): refers to a suspected and unintended serious adverse reaction with the nature and severity of clinical manifestations beyond the existing data and information in investigator brochure of investigational vacccine, package inserts of drugs on market or summary of product characteristics, etc.

# 10.4 Follow-up of adverse events

The investigator should follow up each adverse event. The laboratory test of clinical indicators shall be retested in time if there are  $\geq$  Grade 1 or clinically significant abnormal items judged by the investigator. For all SAEs and AEs with relevance which still exist until the end of AE/SAE collection and record, the investigator should follow up to:

- The event is solved or resumes to the status of baseline or is stable:
- The investigator can confirm that there will be no further improvement;
- No more information can be obtained (the subject refuses to provide more information, or there is evidence which proves that the subject is lost to follow-up even if the investigator has tried his/her best).

During the study, the recovery time (with date) of adverse event should be recorded in AE eCRF and the patient's medical record to verify the original data.

For serious adverse events, adverse events of special interest and pregnancy events, the Fosun or other designated personnel can obtain more case information through telephone, fax, e-mail and/or supervising to perform independent medical assessment for these cases.

The AE original data records updated after the lock of database are available for backup. SAE information needs to be filled in the Serious Adverse Event Report Form as detailed as possible, which is reported to PV department.

#### 10.5 Treatment of reactions and adverse events

Treatment of any reaction or AE is at the sole discretion of the Investigator and according to local standard of care.

# Mitigation plans for specific reactions

Based on experience with other BioNTech RNA-based vaccines, it is anticipated that subjects may experience TEAEs of flu-like symptomatology and/or injection site reactions following the administration of RNA vaccines due to the mechanism of action of RNA-vaccines. This may include fever, chills, rigors, tachycardia, arthralgia, myalgia, headache, nausea. Treatment of these events is dependent on the discretion of the investigators; however, the following management suggestions are provided:

- Treat fever with acetaminophen or nonsteroidal anti-inflammatory drug (NSAIDs) with a dose recommended by the investigational site.
- After the first occurrence of flu-like symptomatology, subjects can be treated with standard therapeutic dose of acetaminophen, or NSAIDs, starting at least 2 h after the immunization.
- Corticosteroids should be avoided as either prophylaxis or treatment as it counteracts the effects of immunization.
- Local injection site reactions can be treated with simple measures such as cooling, antipyretics, analgesics.

Ensure adequate hydration of trial subjects on the day of immunization. Consider administering fluids (e.g., water for drinking, 0.5 - 1.0 L) within approximately 2 h following the immunization according to the standard of investigational site.

If subjects experience enhanced respiratory disease or progression of flu-like symptomatology, such as non-resolution of the symptoms after 7 d, symptom changes that are inconsistent with a relationship to RNA immunization, additional diagnostic measures should be considered and the medical supervisor should be informed.

#### 10.6 Outcome of adverse events

The investigator should determine the outcome of adverse events according to its prognosis. The outcome of adverse events is as follows:

- Recovered/resolved: The subject is fully recovered from AE, without any residual influence or damage.
- Recovering/resolving: The signs and symptoms related to the event are relieved but have not disappeared completely.
- Recovered/resolved with sequelae: The subject is recovered, still with residual influence or damage. The residual influence may be temporary, but still exists at the time of report. If

these sequelae are not considered permanent, new information should be provided at followup when there is change of the event.

- Unchanged: The signs and symptoms related to the event are not relieved. The condition of the subject remains unchanged.
- Aggravated: The signs and symptoms related to the event are not relieved. The condition of the subject is aggravated.
- Fatal: Only when the death is resulted from SAEs, the *fatal* can be chosen as an outcome. All other AEs/SAEs which exist at death should be reported.
- Unknown: It refers to a situation when the subject is lost to follow-up and the investigator cannot confirm the outcome.

# 11.0 Monitoring Committee

# 11.1 Safety Review Committee (SRC)

Safety Review Committee (SRC) will be established comprising investigators, Fosun medical representatives, and medical monitor, etc.

Key roles of the SRC are as follows:

- Before progression to the next age group (elderly group), assess the safety and tolerability data of the subjects in the adult group completed safety visits up to 14 days after prime vaccination, and decide whether to approve initiation of the dose cohort of elderly group. Data collected include vital signs, TEAEs, local reactions, blood/clinical laboratory data, and brief physical examination outcome.
- Before each dose cohort begins boost vaccination, for each dose cohort, assess the safety and tolerability data of the prime vaccination of subjects (including data collected at least up to 14 days post-vaccination) and, decide whether to approve initiation of boost vaccination of this dose cohort. Data collected include vital signs, TEAEs, local reactions, blood/clinical laboratory data, and brief physical examination outcome.
- Throughout the trial, assess whether to replace trial subjects permanently discontinued due to safety issues.
- Throughout the trial, the SRC may specific additional dose levels to be tested and an appropriate regime for enrollment and safety oversight.

See SRC charter for more information. The SRC will act according to written procedures described in SRC charter.

#### 11.2 Independent Data Monitoring Committee (IDMC)

The study will be overseen by an Independent Data Monitoring Committee (IDMC). IDMC will consist of 3 or 5 independent members (including epidemiologist, clinical experts, and statistical expert) and 1 independent non-voting statistician.

The IDMC is required to review the unblinded data when a significant event or risk that could cause the study to be suspended occurs. Based on the results of the safety data review, IDMC can request the suspension of investigation in a certain dose group/age group, or suspension of boost vaccination, and can also provide recommendations for subsequent development based on the periodical study data. This study will proceed in accordance with the protocol-specified procedures if no IDMC recommendation for suspension or modification is received.

The IDMC meetings will consist of open and closed face-to-face meetings or teleconference calls. The type and frequency of scheduled meetings will depend on the subject enrollment and safety event rates. Unscheduled ad hoc meetings will occur if a stopping rule occurs, or at any time consultation is requested by the Pharmacovigilance Study Team.

The IDMC will review safety data on an ongoing basis, except at regular review time points. When the reported AEs meet with the dose-limiting toxicity (DLT) criteria, the IDMC will review all relevant safety data and consider a possible pause of the study, if it deems necessary:

See IDMC charter for more information. The IDMC will act according to written procedures described in IDMC charter.

